#### 10.3.6 Safety

#### 10.3.6.1 Adverse Events

An adverse event (AE) is as any clinically significant unfavorable and unintended medical occurrence, including any abnormal sign (e.g., physical exam), symptom, or disease, whether or not it is considered related to the device being studied in a subject.

Adverse event severity will be graded from 1-5, according to the Common Terminology Criteria for Adverse Events (CTCAE) (Version 4.0) as provided by the US Department of Health and Human Services, NIH, and the National Cancer Institute.

Adverse Events will be categorized with respect to relationship to the device as "not related", "possibly related", "probably related", or "definitely related", as well as by degree of severity.

Statistical Analysis Dlan	Client/Project	BioProtect BP-007
Statistical Analysis Flan	Version and Date	V2 05-DEC-2021

AEs will be characterized by CEC adjudication, when available, for marking/implantation procedurerelatedness, device-relatedness, IMRT-relatedness, rectum-relatedness, and seriousness. Marking/implantation procedure relatedness adjudication will be further subdivided into relatedness to ProSpace implantation, marker implantation, administration of anesthesia, and use of foley catheter. If there are AEs for which the CEC determination for procedure relatedness or seriousness differs from the determination of the study site, the site-reported AE determinations will be listed separately.

Any AEs reported prior to the marking/implantation procedure will be listed as medical history. AEs that begin during or after the marking/implantation procedure will be counted and listed as AEs. If an AE is specified as starting before the marking/implantation procedure, any event with an increase in severity reported during or after the procedure will be counted and listed as an AE. All AEs will be summarized by treatment group.

Unless otherwise specified, summary counts of AEs will be the number of subjects reporting AEs and not the number of events reported. If the same AE is reported multiple times for the same subject, it will only appear once for that specified treatment and category in the summary tables.

The following AE summaries will be provided:

- Overall Summary of AEs, which will summarize all events, all device-related events, all procedure-related events, all serious events, all device-related serious events, and all procedure-related serious events
- All AEs by Type
- All AEs by Type and Timing (based on AE start date) (1-30 days, 31-210 days, and greater than 210 days post-marking/implantation)
- Device-Related AEs by Type
- Procedure-Related AEs by Type
- Severe AEs of all Type
- Unanticipated Adverse Device Effects, if any
- Adverse Events with Site-CEC Differences

#### 10.3.6.2 Perineal Healing Status

Perineal healing status will be summarized as "healed", "healing", or "infected" with descriptive statistics for both groups. Summaries will be provided with frequencies and percentages for each week of IMRT, as well as for the final IMRT visit. Since the timing of the final IMRT visit is subject-dependent, the length of IMRT in weeks will also be summarized by number of subjects (N), mean, median, standard deviation, minimum, and maximum.

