2.2.6.7.2 IMRT Treatments

In general, *for both groups*, IMRT (XRT) must start no more than 24 days after marking/ implantation. Sites will perform a weekly positioning verification using Cone beam or low dose CT scan. For the *Balloon Group*, scan results will also be used to verify balloon spacing of at least 10 mm. Subjects will receive IMRT based on the sites' dose-fractionation schedule. The following data will be captured for *both groups* during the last day of a weekly visit, for as many weeks as the treatment lasts:

IMRT Data Collection:

This data should be captured once per week on the last day of that weeks' treatment sessions during active IMRT treatment.

Weekly

- For *Balloon Group* verification of spacing status as at least 10 mm (from prostate to rectum);
- Changes in medications;
- Expanded Prostate Cancer Index (EPIC) assessment (done once at mid-point assuming the treatment plan exceeds one month (4 weeks));
- Perineal access site healing status (until healed) and
- Adverse events as defined by Sections 2.3.6 and 2.3.7 of this Protocol.

Last XRT Visit

- CT scan taken as described in Section 2.2.4 for the *Balloon*;
- Changes in medications;
- Expanded Prostate Cancer Index (EPIC) assessment and
- Adverse events as defined by Sections 2.3.6 and 2.3.7 of this Protocol.

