2.2.8 DATA COLLECTION SUMMARY

Time Point	Pre-implantation ¹	Implantation	Post- Implantation ⁴	IMRT ⁵ Treatments	IMRT Follow-up
Informed Consent	X ¹				
Medical History & Physical Examination ¹	X ¹				
AUA Symptom Score	X ¹				
Broad Spectrum Antibiotics	X ²				
Randomization	X ³				
Medications	X ¹			Х	Х
CT as per Section 2.2.4 as indicated ⁶	Х		X	Х	Х
Perineal Healing Status (until healed)				Х	
EPIC Assessment ⁷	Х			Х	Х
Adverse Events		As Needed			
Study Completion/ Termination		As Needed			

Study windows:

- 1. Pre-implantation evaluations.
- 2. Broad-spectrum antibiotics must be started 2 days prior to implantation and continued for a total of 5 days.
- 3. Randomization may occur up to 30 days prior to implantation to allow for facility set up and must occur prior to the pre-implantation CT scan.
- 4. The Post-implantation period begins at discharge from the facility and extends to the first IMRT treatment.
- 5. IMRT treatments must start no more than 24 days after marking/ implantation and data will be collect weekly on the last day of that week's visits.
- 6. CT is taken for the *Balloon Group* up to 30 days pre-implantation and post-implantation, at the last XRT visit and at the 6-month F/U visit. Additionally, CT may be taken in the *Balloon Group* at 12 months if remnants of the balloon remain at 6 months. A CT will be taken in the *Control Group* post-implantation.
- 7. EPIC is taken at baseline, at mid XRT treatment (assuming the treatment plan is for greater than one month) on last XRT day and at every follow-up visit thereafter.

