#### 7.1 Table 1. Data Collection Summary

Time Point	Pre-implantation 	Implantation	Post- Implantation 	IMRT Treatments 	IMRT Follow-up 
Informed Consent	X 				
Medical History & Physical Examination 	X 				
AUA Symptom Score	X 				
Broad Spectrum Antibiotics	X 				
Randomization	X 				
Medications 	X 			Х	Х
CT 	X		Х	Х	Х
Perineal Healing Status (until healed) 				Х	
EPIC Assessment 	X			Х	Х
Adverse Events		As Needed			
Study Completion/ Termination		As Needed			

Study windows:

- 1. Pre-implantation evaluations.
- 2. Broad-spectrum antibiotics must be started 2 days prior to implantation and continued for a total of 5 days.
- 3. Randomization may occur up to 30 days prior to implantation to allow for facility set up and must occur prior to the pre-implantation CT scan.
- 4. The Post-implantation period begins at discharge from the facility and extends to the first IMRT treatment.
- 5. IMRT treatments must start no more than 24 days after marking/implantation and data will be collected weekly on the last day of that week's visits.
- 6. Medications, perineal healing status (until healed), and verification of spacing status (*ProSpace Group*) are captured once per week during active IMRT treatment on the last day of that week's treatment sessions.
- 7. CT will be taken for the *ProSpace Group* up to 30 days pre-implantation and post-implantation, at the last XRT visit and at the 6-month follow-up visit. Additionally, CT may be taken in the *ProSpace Group* at 12 months if remnants of the balloon remain at 6 months. CT will be taken in the *Control Group* post-implantation.
- 8. EPIC will be taken at baseline, at mid XRT treatment (assuming the treatment plan is for greater than one month), on last XRT day, and at every follow-up visit thereafter.
- 9. The subject will be seen at 6 months (± 2 weeks) and every 6 months thereafter (± 4 weeks) from the time of marking/implantation until the last subject has completed 6 months of follow-up.

Statistical Analysis Dlan	Client/Project	BioProtect BP-007
Statistical Analysis Flan	Version and Date	V2 05-DEC-2021

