# **10** Statistical Methods

## **10.1 General Statistical Considerations**

Study data will be made available in listings or electronic files, and study data will be listed by subject with the randomized treatment indicated. The study results will be summarized using descriptive statistics by randomized treatment. Summaries of baseline information will also include a total column. Standard numeric descriptive statistics include the n (observed values), mean (including the 95% confidence interval), standard deviation, median, minimum, and maximum values. Categorical data will be summarized with counts and percentages calculated based on non-missing values. Measures summarized across multiple visits will be summarized by visit, and a change from baseline will be provided for numeric variables.

A two-sided p-value of less than or equal to 0.05 or a one-sided p-value of less than or equal to 0.025 will be considered statistically significant unless otherwise specified.

All statistical analyses and summaries will be generated using SAS version 9.4.

<sup>1 HHS, FDA (1998). Guidance for industry: E9 Statistical Principles for Clinical Trials

<sup>2 SAS software. Version 9.4. Copyright © 2016 SAS Institute Inc., Cary, NC, USA.

Statistical Analysis Dlan	Client/Project	BioProtect BP-007
Statistical Allalysis Flan	Version and Date	V2 05-DEC-2021

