#### **Handling of Missing Data**

The handling of missing data from the primary safety and efficacy analyses is addressed through the sensitivity analyses identified in Sections 10.3.4.1.3 and 10.3.4.2.3. All other summaries will be based on available data, without imputation of missing data.

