#### Tables

Table 14.2.9.2, Analysis of EPIC Sexual Domain Scores at IMRT Midpoint and Final IMRT Visit, Per-Protocol
Population
Table 14.3.1.1, Overall Summary of Adverse Events, Per-Protocol Population
Table 14.3.1.2.1, Adverse Events by Term, Per-Protocol Population
Table 14.3.1.2.2, Adverse Events by Term and Timing, Per-Protocol Population
Table 14.3.1.3.1, Device-Related Adverse Events Term, Per-Protocol Population
Table 14.3.1.3.1, Device-Related Adverse Events Term and Timing, Per-Protocol Population
Table 14.3.1.4.1, Procedure-Related Adverse Events by Term, Per-Protocol Population
Table 14.3.1.4.2, Procedure-Related Adverse Events by Term and Timing, Per-Protocol Population
Table 14.3.1.5.1, Adverse Events Rated as Serious by Term, Per-Protocol Population
Table 14.3.1.5.2, Adverse Events Rated as Serious by Term and Timing, Per-Protocol Population
Table 14.3.1.6.1, Device-Related Adverse Events Rated as Serious by Term, Per-Protocol Population
Table 14.3.1.6.2, Device-Related Adverse Events Rated as Serious by Term and Timing, Per-Protocol Population
Table 14.3.1.7.1, Procedure-Related Adverse Events Rated as Serious by Term, Per-Protocol Population
Table 14.3.1.7.2, Procedure-Related Adverse Events Rated as Serious by Term and Timing, Per-Protocol
Population
Table 14.3.2.1, AEs by CTCAE Grade, Per-Protocol Population
Table 14.3.2.2, Device-Related Severe Adverse Events by Term, Per-Protocol Population
Table 14.3.2.3, Procedure-Related Severe Adverse Events by Term, Per-Protocol Population
Table 14.3.3.1, Listing of Adverse Events Leading to Study Discontinuation, Per-Protocol Population
Table 14.3.3.2, Listing of Adverse Events Leading to Death, Per-Protocol Population
Table 14.3.4.1, Perineal Healing Status Each Week During Radiation Therapy, Per-Protocol Population
Table 14.3.4.2, Perineal Healing Status at Final Radiation Therapy Visit, Per-Protocol Population

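### Perineal healing is recorded only until healed, but the SAP tabulates it every IMRT week over non-missing values, so men already healed drop out of the later percentages (descriptive tables; minor)

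*SAP*

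**What the plan says.** **Collection.** The weekly IMRT list in Protocol 2.2.6.7.2 closes with "Perineal access site healing status (until healed) and" adverse events. The schedule in Protocol 2.2.8 carries the same limit and marks the item only in the IMRT treatments column. Footnote 6 of SAP Table 1 repeats it: "Medications, perineal healing status (until healed), and verification of spacing status" are captured once a week during active IMRT. None of these places asks for a further record once a man has healed.

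**Reporting.** SAP 10.3.6.2 uses three categories (healed, healing, infected) for both groups, and adds: "Summaries will be provided with frequencies and percentages for each week of IMRT, as well as for the final IMRT visit". The SAP's table list includes "Table 14.3.4.1, Perineal Healing Status Each Week During Radiation Therapy, Per-Protocol Population" and a companion, Table 14.3.4.2, for the final radiation visit.

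**Denominator and missing data.** SAP 10.1 states: "Categorical data will be summarized with counts and percentages calculated based on non-missing values". Its missing-data paragraph sends the primary endpoints to their own sensitivity analyses and continues: "All other summaries will be based on available data, without imputation of missing data". SAP 10.3.6.2 makes no exception to either rule.

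**The concern.** The collection rule and the reporting rule do not fit together. Collection treats healing as an end state, after which nothing more is recorded. Reporting treats it as a status observed every week. With a non-missing denominator and no carry-forward, the men who have done well disappear from the table.

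A reader of a table of weekly healing status will take the healed column as the share of the arm that has healed. It would instead be a weekly healing rate among slower healers, which can stay flat or fall while the true share rises. The infected percentage would be divided by the same shrinking group. These two tables are the only planned summary of access-site healing, and Protocol 2.3.6.1 lists site infection among the marking and implantation risks, so a misread percentage could make the procedure look worse than it was.

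**Working it through.** The plan states no figure for this point, so there is nothing to reproduce. The check is to apply the written rules to an assumed cohort.

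**Formulas.** Let N be the men in an arm, all still in IMRT; U(w) those not healed by the end of week w; H(w) those newly healed in week w; I(w) those infected in week w.

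- Records in week w: N for w = 1, then U(w−1).
- Percentages as written: healed = H(w)/U(w−1); infected = I(w)/U(w−1).
- Share of the arm: healed = (N − U(w))/N; infected = I(w)/N.
- The infected percentage is therefore inflated by N/U(w−1).

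**Worked example.** N = 148 is the planned balloon group (Protocol 2.3.4.4.2). All healing and infection numbers are assumed: 120 men healed in week 1, 14 of the remaining 28 in week 2, 7 of the remaining 14 in week 3, and 2 infected in week 3.

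| IMRT week | Records | Healed, as written | Healed, share of arm |
|---|---|---|---|
| 1 | 148 | 120/148 = 81% | 120/148 = 81% |
| 2 | 28 | 14/28 = 50% | 134/148 = 91% |
| 3 | 14 | 7/14 = 50% | 141/148 = 95% |

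Infected in week 3: 2/14 = 14% as written, against 2/148 = 1.4% of the arm. The count is 2 either way. Week 1 is sound here because every man has a record that week; the distortion starts with the second recorded week.

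**Range.** Let p be the share healed in week 1 and q the share of unhealed men who heal in each later week. Week 3 then prints q, while the true share is 1 − (1 − p)(1 − q)². Take p from 50% to 95% and q from 40% to 60%:

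- printed: 40% to 60%;
- lowest true share: 1 − 0.50 × 0.60² = 82%;
- highest true share: 1 − 0.05 × 0.40² = 99%.

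**Final visit.** Assume an eight-week course (78 Gy in 2 Gy fractions is 39 fractions, or 7.8 weeks at an assumed five a week), p = 80% and q = 30% to 50%. Expected records in week 8 are 148 × 0.20 × (1 − q)⁶, which is 3.5 men at q = 30% and 0.5 at q = 50%. The true share healed by then is 1 − 0.20 × (1 − q)⁷, or 98.4% to 99.8%. Table 14.3.4.2 would rest on almost nobody.

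**Between arms.** With the same p and q in both arms, the expected percentages are the same whether N is 148 or 74, so the comparison is not biased. With different p it can mislead. At q = 50%, p = 80% in one arm and 95% in the other, week 2 prints 50% healed in both, against true shares of 90% and 97.5%. The infected percentage would be inflated 1/0.20 = 5-fold in one arm and 1/0.05 = 20-fold in the other.

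**The case against.** The best defence is that a man already healed has no missing value: the protocol asks nothing more of him, so his later status is not applicable, and his earlier healed record is available data. A healed category at the final visit makes most sense if healing is meant to last. The shells are in a separate document (SAP section 13) and the eCRF is not in the file; either could supply the right denominator. That reading is possible, so it cannot be said that the SAP forbids carrying the status forward. But no visible text says to do so, and a programmer following SAP 10.1 literally would produce the percentages above.

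Other points in the plan's favour stand. SAP 10.3.6.2 requires frequencies as well as percentages, so a row with 28 records in an arm of 148 would show its own small base. If nearly everyone has healed by the first IMRT week, which can start up to 24 days after marking, later rows would be close to empty rather than persuasive.

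A reader might infer three stronger things that the documents do not support:

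- *That infection reporting as a whole is compromised.* Recorded infected counts do not change, and infections reported as adverse events also enter the AE tables by term and timing and, where so adjudicated, by procedure relatedness (SAP 10.3.6.1). An infection arising after a healed record would be missed by the healing table, but remains reportable as an adverse event.
- *That the arms are necessarily distorted differently.* That holds only if they heal at different speeds, and the documents give no healing rates.
- *That omitting healing status from the protocol's Last XRT Visit list leaves unhealed men unassessed.* The weekly list, captured on the last treatment day of each week, already covers them in the final week.

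**Conclusion.** The point holds as a minor correction. Under the rules as written, and unless the shells or eCRF provide otherwise, the healed percentage from the second recorded week is the share newly healed among men not yet healed, and the infected percentage has the same shrinking denominator. Under the assumed rates the gap is large, but its true size cannot be known from the documents.

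The consequence is limited. The tables are descriptive. Neither co-primary endpoint, no secondary endpoint, the sample size and none of the labeling comparisons uses them. A reader might infer that the trial's safety conclusion is at risk; nothing in the plan connects these tables to it.

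**What to change.** Add to SAP 10.3.6.2:

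- A subject recorded as healed is counted as healed at every later IMRT week and at the final IMRT visit, unless a later record or adverse event shows otherwise.
- The denominator for each week is all PP subjects still in IMRT that week.
- Table 14.3.4.2 reports the number and percentage healed at or before the final IMRT visit.

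State that this derivation takes precedence over the general non-missing and no-imputation rules in SAP 10.1, and carry it into the table shells. The cost is a few lines of SAP text and a simple programmed derivation. It needs no new data, no extra visit and no change to how subjects are managed.

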#### 10.3.6.3 Physical Examination

Physical examination results will be provided in by-subject listings including clinically significant abnormalities.

# 12 List of Tables, Figures and Listings

Tables
Table 14.1.1.1, Study Enrollment, All Subjects
Table 14.1.1.2, Study Enrollment by Site, Intent-to-Treat Population
Table 14.1.1.3, Subject Follow-Up, Per Protocol Population
Table 14.1.1.4, Protocol Deviations, Per-Protocol Population
Table 14.1.2.1, Demographics, Per-Protocol Population
Table 14.1.2.2, Demographics, Intent-to-Treat Population
Table 14.1.3.1, Medical History, Per-Protocol Population
Table 14.1.3.2, Medical History, Intent-to-Treat Population
Table 14.1.3.3.1, Medications at Screening, Per-Protocol Population
Table 14.1.3.3.2, Medications at During Study, Per-Protocol Population
Table 14.1.4.1, Study Procedure Information, Per-Protocol Population
Table 14.1.4.2, Study Procedure Information, Intent-to-Treat Population
Table 14.2.1.1, Primary Analysis of Reduction in V Rectum 70, ProSpace Per-Protocol Population
Table 14.2.1.2, Tipping Point Analysis of Reduction in V Rectum 70, ProSpace Intent-to-Treat Population
Table 14.2.1.3, Covariate Analyses for Reduction in V Rectum 70, ProSpace Per-Protocol Population
Table 14.2.1.4, Summary of Percentage Reduction in V Rectum 70, ProSpace Per-Protocol Population
Table 14.2.1.5, Dosimetry Parameters, ProSpace Per-Protocol Population
Table 14.2.1.6, Rectal Wall Distance, ProSpace Per-Protocol Population
Table 14.2.2.1, Primary Safety Analysis for Occurrence of Grade 1 or Greater Rectal Adverse Events, Per-Protocol
Population
Table 14.2.2.2, Primary Safety Analysis for Occurrence of Grade 1 or Greater Rectal Events Tipping Point
Analysis, Per-Protocol Population
Table 14.2.2.3, Primary Safety Endpoint Cumulative Safety Events by Time Kaplan-Meier Estimates, Per-Protocol
Population
Table 14.2.2.4, Covariate Analyses for Reduction in Primary Safety Endpoint Using Kaplan-Meier Method, Intent-
to-Treat Population
Table 14.2.2.5, Sensitivity Analysis for Occurrence of Grade 1 or Greater Rectal Events through Day 197, Per-
Protocol Population, Per-Protocol Population
Table 14.2.3, Analysis of Grade 2 or Greater Rectal or Procedure-Related Events of Duration of Two or More
Days, Per-Protocol Population
Table 14.2.6.1, Analysis of EPIC Urinary Incontinence Domain Scores by Timepoint, Per-Protocol Population
Table 14.2.6.2, Analysis of EPIC Urinary Incontinence Domain Scores at IMRT Midpoint and Final IMRT Visit,
Per-Protocol Population
Table 14.2.7.1, Analysis of EPIC Urinary Irritative Domain Scores by Timepoint, Per-Protocol Population
Table 14.2.7.2, Analysis of EPIC Urinary Irritative Domain Scores at IMRT Midpoint and Final IMRT Visit, Per-
Protocol Population
Table 14.2.8.1, Analysis of EPIC Bowel Domain Scores by Timepoint, Per-Protocol Population
Table 14.2.8.2, Analysis of EPIC Bowel Domain Scores at IMRT Midpoint and Final IMRT Visit, Per-Protocol
Table 14.2.9.1, Analysis of EPIC Sexual Domain Scores by Timepoint, Per-Protocol Population

Client/Project	BioProtect BP-007
Version and Date	V2 05-DEC-2021

#### Tables

Table 14.2.9.2, Analysis of EPIC Sexual Domain Scores at IMRT Midpoint and Final IMRT Visit, Per-Protocol
Population
Table 14.3.1.1, Overall Summary of Adverse Events, Per-Protocol Population
Table 14.3.1.2.1, Adverse Events by Term, Per-Protocol Population
Table 14.3.1.2.2, Adverse Events by Term and Timing, Per-Protocol Population
Table 14.3.1.3.1, Device-Related Adverse Events Term, Per-Protocol Population
Table 14.3.1.3.1, Device-Related Adverse Events Term and Timing, Per-Protocol Population
Table 14.3.1.4.1, Procedure-Related Adverse Events by Term, Per-Protocol Population
Table 14.3.1.4.2, Procedure-Related Adverse Events by Term and Timing, Per-Protocol Population
Table 14.3.1.5.1, Adverse Events Rated as Serious by Term, Per-Protocol Population
Table 14.3.1.5.2, Adverse Events Rated as Serious by Term and Timing, Per-Protocol Population
Table 14.3.1.6.1, Device-Related Adverse Events Rated as Serious by Term, Per-Protocol Population
Table 14.3.1.6.2, Device-Related Adverse Events Rated as Serious by Term and Timing, Per-Protocol Population
Table 14.3.1.7.1, Procedure-Related Adverse Events Rated as Serious by Term, Per-Protocol Population
Table 14.3.1.7.2, Procedure-Related Adverse Events Rated as Serious by Term and Timing, Per-Protocol
Population
Table 14.3.2.1, AEs by CTCAE Grade, Per-Protocol Population
Table 14.3.2.2, Device-Related Severe Adverse Events by Term, Per-Protocol Population
Table 14.3.2.3, Procedure-Related Severe Adverse Events by Term, Per-Protocol Population
Table 14.3.3.1, Listing of Adverse Events Leading to Study Discontinuation, Per-Protocol Population
Table 14.3.3.2, Listing of Adverse Events Leading to Death, Per-Protocol Population
Table 14.3.4.1, Perineal Healing Status Each Week During Radiation Therapy, Per-Protocol Population
Table 14.3.4.2, Perineal Healing Status at Final Radiation Therapy Visit, Per-Protocol Population

